11.5.2 Relapse (progression) – free Survival (RFS/PFS)

Relapse-free survival is defined as the proportion of patients who remain free of AML recurrence (hematologic) and alive. According to current WHO classification, a myeloblast population comprising greater than 5% of nucleated cells in the bone marrow or blood is required for diagnosis of AML relapse following CR/CRi (if no peripheral blasts are present, then a confirmation aspirate is required ≥ 1 week subsequent to the aspirate at which $>5\%$ blasts were identified). RFS will be evaluated via Kaplan-Meier analysis (in which patients who are lost to follow-up or who are not evaluable for recurrence have data censored), and via direct proportional analysis (percentage of patients receiving treatment [or treatment at MTD or otherwise derived Stage 2 dose] who are alive and without evidence of AML recurrence). Median, 6- and 12-month RFS rates will be evaluated.

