4.3.2. Relapse-Free Survival

Relapse-Free Survival is defined as the time from the date of first infusion of Tagraxofusp to the date of relapse (AML recurrence) or death from any cause, whichever occurred first. According to current WHO classification, a myeloblast population comprising greater than 5% of nucleated cells in the bone marrow or blood is required for diagnosis of AML relapse following CR/CRi

(if no peripheral blasts are present, then a confirmation aspirate is required ≥ 1 week subsequent to the aspirate at which $>5\%$ blasts were identified).

For patients who receive SCT, RFS will include time to progressive disease or death post-transplant. Patients who do not progress and are still alive at the time of analysis will be censored on the date of last treatment recorded prior to the analysis cut-off date. If patients start other anticancer therapies (with the exception of SCT or preparations for SCT), they will be censored at the latter of the date of last treatment with Tagraxofusp or date of last disease assessment recorded that occurred prior to the start of the new therapy.

The proportion of subjects receiving treatment who are alive and without evidence of AML recurrence will be presented. The distribution for RFS will be estimated by Kaplan-Meier methodology and the 25th percentile, median, 75th percentile, number and percentage of events and censored observations, and appropriate CIs will be presented. 6- and 12-month RFS rates will be evaluated.

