5. CHANGES TO PLANNED ANALYSES

As of this date, there have been no changes between the protocol-defined statistical analyses and those presented in this statistical analysis plan. All changes from procedures outlined in this SAP will be summarized in the study report. Decisions to deviate from planned analyses will be documented at the time they are made.

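### SAP 4.3.2 censors RFS at new non-transplant therapy, a rule absent from protocol 11.5.2 and not declared in SAP Section 5; its effect depends on why that therapy is started

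*SAP*

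**What the plan says.** - **Protocol 11.5.2** plans a Kaplan-Meier analysis of RFS "in which patients who are lost to follow-up or who are not evaluable for recurrence have data censored". It has no rule for new therapy or for stem cell transplant (SCT). It adds a second analysis "via direct proportional analysis", the share of treated patients alive with no recurrence.
- **SAP 4.3.2** measures RFS from first infusion "to the date of relapse (AML recurrence) or death from any cause, whichever occurred first". Starting another therapy is not an event.
- **SAP 4.3.2, transplant:** "For patients who receive SCT, RFS will include time to progressive disease or death post-transplant".
- **SAP 4.3.2, other therapy:** "If patients start other anticancer therapies (with the exception of SCT or preparations for SCT), they will be censored". The censoring date is the later of the last dose and the "date of last disease assessment recorded that occurred prior to the start of the new therapy".
- **SAP 4.3.2, event-free patients:** those alive without progression "will be censored on the date of last treatment recorded prior to the analysis cut-off date".
- **SAP 4.3.2** also keeps the crude proportion and reports 6- and 12-month RFS rates. It plans no analysis without the new-therapy rule.
- **SAP Section 5** states that "there have been no changes between the protocol-defined statistical analyses and those presented in this statistical analysis plan".

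**The concern.** The SAP adds a reason for censoring that the protocol does not contain, while stating that nothing has changed.

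Kaplan-Meier estimation assumes that a censored patient has the same outlook as those still at risk. That assumption is doubtful in this trial. Stage 2 patients are enrolled because they have minimal residual disease (MRD). Protocol 7.4 bars other anti-leukemia therapy until SL-401 stops, and protocol 7.6.1 lists recurrence or progression among the reasons for stopping. At least three kinds of failing patient could be censored rather than counted:

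- a patient treated for rising MRD while still in hematologic remission;
- a patient with more than 5% marrow blasts and no peripheral blasts who starts therapy before the confirmation aspirate, due at least one week later;
- a patient treated for progressive disease under Appendix A (falling counts, transfusion dependence), which is not in itself the RFS event.

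Any later relapse or death in these patients would not enter the curve. At stake are the 6- and 12-month RFS rates of a small single-arm trial, where one or two reclassified patients change the reported figure.

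**Working it through.** **The plan's own figures.** The documents give no RFS rate, event count or power to reproduce. The only design figures concern the MRD rule (at least 2 of 15, 5% against 20%), and they reproduce:
- type 1 error = 1 − 0.95^15 − 15(0.05)(0.95^14) = 0.171 (stated 17%);
- power = 1 − 0.8^15 − 15(0.2)(0.8^14) = 0.833 (stated above 80%).

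They do not bear on RFS.

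**Inputs.** Protocol 3.1.3 cites a 1-year relapse rate above 60% in intermediate-risk patients with MRD, so 12-month RFS is assumed to be 40%. Stage 2 enrolled 9 patients (SAP 3.1). The share of relapses preceded by new therapy, q, is not in the documents; 10% to 30% is assumed.

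**Size if therapy anticipates relapse.** Censoring a fraction q of events just before they occur multiplies the hazard by (1 − q), so the curve estimates S^(1−q):
- q = 10%: 0.4^0.9 = 0.438
- q = 20%: 0.4^0.8 = 0.480
- q = 30%: 0.4^0.7 = 0.527

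The standard error at n = 9 is √(0.4 × 0.6 / 9) = 0.163. The shifts of 3.8, 8.0 and 12.7 points are therefore 0.2, 0.5 and 0.8 standard errors. From an assumed 30%, the same formula gives 34% (0.3^0.9) to 43% (0.3^0.7).

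**Dependence on why therapy starts.** Simulation of 100,000 patients, assuming exponential RFS with 40% at 12 months, 24 months of follow-up, assessments near months 2, 4, 6, 9 and 12 and then every 3 months, and last dose between 0.15 and 4.8 months. Entries are 6-/12-month RFS in percent. Except in the last two rows, only the new-therapy rule is applied.

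| Rule and reason for therapy | Lowest use | Middle | Highest use |
|---|---|---|---|
| Protocol rule | 63.2/40.0 | 63.2/40.0 | 63.2/40.0 |
| Started within 1 month before relapse, no effect on relapse time (10, 20, 30% of patients) | 66.0/43.5 | 69.0/47.3 | 72.1/51.6 |
| Timing unrelated to prognosis (7, 14, 21%) | 63.0/39.8 | 62.8/39.6 | 62.4/39.1 |
| Started by patients doing well (8, 16, 24%) | 62.7/36.3 | 62.0/31.5 | 61.3/24.9 |
| Full SAP rule, therapy shortly before relapse (10, 20, 30%) | 62.5/34.7 | 66.0/39.6 | 69.8/45.1 |
| Last-treatment censoring only | 59.0/30.1 | 59.0/30.1 | 59.0/30.1 |

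If therapy started shortly before relapse delays it by 6 months, the protocol rule itself gives 67.0/42.3, 70.6/44.5 and 74.1/46.9, against 66.0/43.5, 68.9/47.2 and 71.9/51.4 under new-therapy censoring. The 12-month gap shrinks to 1.2, 2.7 and 4.5 points, and the 6-month figure falls slightly below the protocol rule.

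**Why last-treatment censoring lowers RFS.** With six undelayed 28-day cycles, the last dose falls on day 5 × 28 + 5 = 145, about 4.8 months. An event-free patient who stops there leaves the risk set before the 6-month landmark, while later relapses in other patients still count.

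**Nine-patient illustration.** Events at 2, 3, 4, 5, 7 and 9 months; three patients event-free at 12.
- Protocol rule: 5/9 = 55.6% at 6 months, 3/9 = 33.3% at 12.
- Relapses at 4 and 5 months censored at months 2 and 4: 8/9 × 6/7 = 76.2%, then × 4/5 × 3/4 = 45.7%.
- In addition, event-free patients censored at 4.8 months: 76.2%, then × 1/2 × 0 = 0%.
- Last-treatment censoring alone: 8/9 × 7/8 × 6/7 × 2/3 = 44.4%, then × 1/2 × 0 = 0%.

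**The case against.** A reader might infer that the SAP rule biases RFS upward whatever happens, and that following transplanted patients adds to the bias. The documents support neither inference.

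- **Direction.** No section gives the frequency of, or reasons for, later therapy without relapse. Protocol 7.6.1 also lists toxicity, intercurrent illness, completion of six cycles and the investigator's decision as reasons to stop SL-401. Depending on the reason, the effect can be upward, near zero or downward. The last-treatment rule pulls the other way: even with therapy started shortly before relapse, the full SAP rule gives 34.7% to 45.1% at 12 months against 40.0%. This objection stands.
- **Transplant.** Protocol 11.5.2 does not censor at SCT, so following patients through it is consistent with the protocol. The SAP counts progression and death after transplant, so harm is kept as well as benefit. This stands too. What remains is an inconsistency: one later therapy is followed through and the others are not.
- **Patients are not discarded.** They contribute time up to censoring. The crude proportion is presented with no stated exclusion for new therapy, OS counts every death, and by-patient listings are planned. This softens the concern but does not repair the Kaplan-Meier 6- and 12-month rates.
- **The protocol's wording is loose.** It does not define non-evaluability for recurrence, which might be stretched to some patients on new therapy. A patient whose marrow is still being assessed does not plainly fit, and the SAP does not present its rule as an interpretation.
- **Low stakes.** RFS is a descriptive secondary endpoint; SAP 3.2 confines formal testing to MRD eradication. That is correct and limits the consequence.

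**Conclusion.** The point holds in a limited form. SAP 4.3.2 contains a censoring rule that protocol 11.5.2 does not, and the no-change statement in SAP Section 5 is wrong for RFS.

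If new therapy is started for impending relapse, the rule inflates 12-month RFS from an assumed 40% to about 44% to 53%, or 0.2 to 0.8 standard errors at n = 9. This assumes that 10% to 30% of relapses are preceded by therapy that does not change their timing; the inflation at 12 months is smaller if therapy delays relapse. The 40% is borrowed from intermediate-risk patients and may be too high for an adverse-risk population.

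The net effect of the whole SAP paragraph has no fixed direction. Removing only the new-therapy rule would not be enough: last-treatment censoring alone gives 30.1% at 12 months in the simulation. With therapy started shortly before relapse, that is further from the protocol rule's 40.0% than the SAP as it stands. The MRD decision rule is not touched.

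**What to change.** 1. In SAP 4.3.2, make the main RFS analysis follow the protocol: count relapse or death at its actual date, regardless of later anticancer therapy or SCT.
2. In the same paragraph, censor event-free patients at their last disease assessment instead of their last treatment. This must accompany step 1.
3. Present censoring at new therapy as a sensitivity analysis, once with SCT censored and once with it uncensored.
4. Declare in SAP Section 5 any censoring rule that departs from protocol 11.5.2.

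**Cost.** SAP wording and a few additional runs, with no new design work. The main estimate will then include effects of later therapy, which the sensitivity analysis shows. One check is needed first. Protocol 9.7 asks for disease status about every 90 days in patients still in remission at end of treatment, but 7.6.2 and the Table 6 footnote describe the 90-day contact as survival status. The sponsor should confirm how much relapse information after new therapy was recorded and report its completeness alongside the estimate.

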4.3.3. Overall Survival

Overall survival is defined as the time from the date of first infusion of Tagraxofusp to the date of death from any cause. Patients still alive or lost to follow-up at the time of the analysis will be censored on the last date known to be alive prior to the analysis cut-off date, as determined by in- person visit or telephone contact. The overall distribution for OS will be estimated by Kaplan-Meier methodology in a similar manner to RFS.

4.4. Safety Analyses

All safety tabulations will be presented by dose received.

4.4.1. Study Drug Exposure

Duration of study drug exposure will be calculated as the number of days and number of cycles patients were administered study drug.

$$\text{Duration of Study Drug Exposure} = (\text{Date of last dose} - \text{Date of first dose}) + 1$$

Duration in cycles of drug exposure will be defined the total number of cycles of study drug initiated while the patient is on study. Total dose administered will be summarized overall and by cycle.

Relative Dose Intensity will be computed using the following definition:

$$\text{Relative Dose Intensity (\%)} = 100 * \frac{\text{Sum(Cumulative Actual Dose Received by Cycle)}}{\text{Sum(Planned Dose to be Administered by Cycle)}}$$

Exposure to Tagraxofusp will be presented in by-patient data listings.

4.4.2. Adverse Events

All AEs will be coded using the MedDRA coding system and displayed in tables and data listings using system organ class (SOC) and preferred term (PT).

Analyses of AEs will be performed for those events that are considered treatment-emergent, where treatment-emergent is defined per protocol as any AE with onset after the first administration of Tagraxofusp through 30 days after the last dose of Tagraxofusp, or any event that was present at baseline but worsened in intensity or was subsequently considered drug-related by the Investigator through 30 days after the last dose of Tagraxofusp.

The number and percentage of patients with any treatment-emergent AE (TEAE), with any TEAE assessed by the Investigator as related to treatment, with any TEAE with severity \geq Common Terminology Criteria for Adverse Events (CTCAE) Grade 3, with any SAE, with any AE leading to discontinuation of study treatment, and with any AE leading to dose modification will be summarized by dose group and overall. In these tabulations, each patient will contribute only once (ie, the most related occurrence or the most intense occurrence) to each of the incidence rates in the descriptive analysis, regardless of the number of episodes.

Treatment-emergent AEs summarized by patient incidence rates are not tabulated by severity or relationship to study treatment; therefore, in such tabulations, a patient contributes only once to the count for a given AE SOC or PT. For tabulations that include classification by relationship to study treatment, AEs with missing relationship will be considered related to study drug.

Adverse events of special interest (AESI's) will be determined using MedDRA version 19.0 standardized medical queries (SMQs), high-level terms, or PTs, as follows:

- Possible hypersensitivity events, based on the SMQ Hypersensitivity (broad search).
- Vascular capillary leak syndrome (CLS), based on the MedDRA SMQ [to be provided] in addition to PTs of hypoalbuminaemia, blood albumin decreased, and proteinuria.
- Possible drug-induced liver injury events, based on the SMQ drug-related hepatic disorders (broad search).

Summary tables of AESIs produced will report AESIs as follows:

- AESIs overall and by PT,
- AESIs by PT overall and by grouped cycle (Cycle 1, Cycles 2-4, Cycles \geq 5),
- \geq 3 Grade AESIs overall and by PT,
- Serious AESIs overall and by PT,
- AESIs resulting in drug interruption overall and by PT,
- AESIs resulting in dose reduction overall and by PT,
- AESIs resulting in study drug withdrawn/ discontinued overall and by PT,

- AESIs resulting in death overall and by PT.

These tabulations will be completed for all AML patients, by dose group. AESIs will also be included in data listings.

4.4.2.1. Capillary Leak Syndrome

In addition to the summaries described in [Section 4.4.2](#), summaries will be provided that include:

- Summary of number and grade of CLS events, exposure to Tagraxofusp prior to onset of CLS, and time to first onset and time to resolution of CSL events.

4.4.3. Laboratory Data

Clinical laboratory values will be expressed in Système International (SI) units.

The actual value and change from baseline (Day 1) to each on-study evaluation through cycle 6 will be summarized for each clinical laboratory parameter, including hematology, clinical chemistry, coagulation, and urinalysis. In the event of repeat values, the last non-missing value per study day/time will be used.

[figure not shown]
Shift tables of change in CTCAE grade of laboratory parameters from baseline to worst value and from baseline to last value on study will be presented. Both scheduled and unscheduled visits will be included in shift tables.

To assess for possible drug-induced liver injury ([FDA 2009](#)), a figure plotting peak alanine aminotransferase (ALT) versus peak total bilirubin (both on a logarithmic scale \times upper limit of normal [ULN]) will be produced similar to that recommended by Watkins et al ([Watkins, et al. 2008](#)) so that values within the normal reference range (<ULN) for ALT and total bilirubin are found in the left lower quadrant and Hy's Law case candidates are in the upper right quadrant (ALT $>3 \times$ ULN and total bilirubin $>2 \times$ ULN). Patients with Gilbert's syndrome or cholestasis are typically found in the upper left quadrant, and patients with ALT elevations without significant hepatic abnormality (ie, without increased total bilirubin) are found in the lower right quadrant. The peak total bilirubin value plotted will be the peak within ± 7 days of the peak ALT value. If at least five patients are identified as potential Hy's Law Cases, a summary table will be produced for the number and percentage of patients who have values of aspartate aminotransferase (AST) (>3 to $\leq 5 \times$ ULN, >5 to $\leq 10 \times$ ULN, >10 to $\leq 20 \times$ ULN, $>20 \times$ ULN), ALT (>3 to $\leq 5 \times$ ULN, >5 to $\leq 10 \times$ ULN, >10 to $\leq 20 \times$ ULN, $>20 \times$ ULN), alkaline phosphatase ($>1.5 \times$ ULN), or total bilirubin (>1.5 to $\leq 2 \times$ ULN, $>2 \times$ ULN) after initiation of study drug. In this table, a patient may be counted only one time. For instance, a patient with a result of AST of $11 \times$ ULN will be counted in the category of >10 to $\leq 20 \times$ ULN.

This plot will be repeated for peak aspartate aminotransferase (AST) by total bilirubin.

An example of the scatterplot is provided in [Figure 4-1](#).

Figure 4-1: Hy's Law Candidates Scatterplot

Time to first onset of elevated AST and ALT will be analyzed using Kaplan-Meier analyses and be presented as figures.

All laboratory data will be provided in by-patient data listings.

A by-patient listing will also be presented for all laboratory values with CTCAE Grade ≥ 3 .

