Hypoalbuminemia (any Grade = 58.7%; Grade ≥ 3 = 0%) and transaminase elevation (any Grade = 50%; Grade ≥ 3 = 25%) were the most common Grade ≥ 3 AE attributed to SL-401, however almost all episodes were transient. Time courses of liver function tests (LFTs) and albumin among the patients treated with Regimen B indicate that LFT elevations tended to peak approximately two weeks after the first infusion of SL-401, while albumin levels, supported by the administration of albumin to patients with serum albumin falling below 3 g/dL, reached a minimum approximately one week after the first infusion. In most cases, levels of the laboratory parameters resolved to near baseline levels by 14-28 days after the first infusion. Other AEs commonly (i.e., any Grade in $\geq 15\%$ of patients) attributed to SL-401 included fever (any Grade

= 29.3%; Grade ≥ 3 = 1.1%), hypocalcemia (any Grade = 25.0%; Grade ≥ 3 = 0%), edema (any Grade = 18.5%; Grade ≥ 3 = 3.3%), and nausea (any Grade = 16.3%; Grade ≥ 3 = 0%).

A single cycle of SL-401 was associated with single agent activity in patients with relapsed or refractory AML, including 2 durable CRs of 8 and >25 months duration and 5 partial responses (PRs). OS also appeared to be improved among the most heavily pretreated AML patients compared with historical survival results. Specifically, in AML patients who had progression through at least two previous therapies (i.e., third-line or greater; n = 35), the median OS was 3.6 months, more than double the historical median OS of 1.5 months ([Giles et al. 2005](#)).

Multiple durable objective responses were also observed among the patients with BPDCN. Among 9 BPDCN patients treated with 12.5 $\mu\text{g}/\text{kg}/\text{day}$ who were evaluable for response, there were 5 CRs (durations of 3, >3 , 5, >7 , and >20 months) and 2 PRs yielding a response rate of 78% (two patients treated with 12.5 $\mu\text{g}/\text{kg}/\text{day}$ and one patient treated with 9.4 $\mu\text{g}/\text{kg}/\text{day}$ were not evaluable for response).

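### The Hy's Law screen rests on one peak-anchored point per patient, so paired ALT/AST and bilirubin elevations in another cycle, or more than 7 days after the peak, can be missed

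*SAP*

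**What the plan says.** SAP 4.4.3 (Laboratory Data) plans "a figure plotting peak alanine aminotransferase (ALT) versus peak total bilirubin", both as multiples of ULN on log scales. Candidates are those in the upper right quadrant, with ALT above 3x ULN and total bilirubin above 2x ULN. The bilirubin coordinate is restricted: "The peak total bilirubin value plotted will be the peak within" ±7 "days of the peak ALT value". The lower right quadrant is described as holding "patients with ALT elevations without significant hepatic abnormality". The plot is repeated with peak AST. The SAP does not state the period over which the peak is taken, and it does not say that the plot is made by cycle.

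The section continues: "If at least five patients are identified as potential Hy's Law Cases, a summary table will be produced". That table has separate categories for AST, ALT, alkaline phosphatase and total bilirubin. It adds "In this table, a patient may be counted only one time", with the example that an AST of 11x ULN goes in the >10 to ≤20x category.

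Other liver outputs are CTCAE shift tables to the worst and last value (unscheduled visits included), by-patient listings of all laboratory data and of Grade ≥3 values, Kaplan-Meier figures of time to first elevated AST and ALT, and adverse-event tables from the broad hepatic SMQ (SAP 4.4.2).

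**The concern.** The rule looks at bilirubin around one ALT value per patient, but patients have many. Protocol 7.5.2 allows up to six 28-day cycles. Protocol 7.5.5.3 stops dosing after ALT or AST above 5x ULN only for the rest of that cycle, so a patient can have a high ALT in Cycle 1 and be exposed again later. Protocol 3.6.1 reports that "LFT elevations tended to peak approximately two weeks after the first infusion of SL-401", so a bilirubin rise at the end of the cycle can fall outside a 7-day window around that peak.

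Such a patient is not merely left out. The plot shows a large ALT with an unremarkable bilirubin, in the region the SAP associates with no significant hepatic abnormality.

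Safety characterisation is a primary objective, and SAP 4.4.2 names possible drug-induced liver injury as an event of special interest. Grade ≥3 transaminase elevation attributed to the drug occurred in 25% of Study 50047 (92 patients, 70 with AML; Protocol 3.6.1). In Study STML-401-0114 the figure was 54% of 26 BPDCN patients for each of ALT and AST (Protocol 3.6.2), in a different disease on 21-day cycles.

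**Working it through.** The plan gives no figure for this rule, so there is nothing to reproduce. The check applies the rule literally, then looks at sampling and at the five-patient trigger.

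**1. The rule applied to constructed records.** All values are assumed, in multiples of ULN. The plotted point is (maximum ALT, maximum bilirubin within 7 days of that day). It is flagged if ALT >3 and bilirubin >2. AST is handled in the same way.

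| Record | Key values | ALT plot | AST plot | Any sample with ALT >3 and bilirubin >2? |
|---|---|---|---|---|
| A: late bilirubin | Day 15: ALT 9, bili 1.0; Day 21: 4, 1.6; Day 28: 3.2, 2.6; AST equal to ALT | (9, 1.6), not flagged | (9, 1.6), not flagged | Yes, Day 28 |
| B: another cycle | Day 15: ALT 10, bili 0.8; Day 71 (Cycle 3): 6, 2.8; AST equal to ALT | (10, 0.8), not flagged | (10, 0.8), not flagged | Yes, Day 71 |
| C: as B, but AST 5 on Day 15 and 7 on Day 71 | as B | (10, 0.8), not flagged | (7, 2.8), flagged | Yes, Day 71 |
| D: bilirubin near the peak | Day 15: ALT 9, bili 2.5; Day 21: 4, 3.0; AST equal to ALT | (9, 3.0), flagged | (9, 3.0), flagged | Yes |

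In A the window runs from Day 8 to Day 22 and stops before Day 28. A and B meet both thresholds on a single sample and are missed on both plots. C is rescued by AST. D is found.

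**2. Sampling.** Post-dosing draws are on Days 8, 15, 21 and 28 (Protocol 7.5.4), each ±3 days (Protocol Tables 5 and 6). The largest permitted gaps are:

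- Day 8 to 15: (15+3) − (8−3) = 13 days
- Day 15 to 21: (21+3) − (15−3) = 12 days
- Day 21 to 28: (28+3) − (21−3) = 13 days

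On nominal days, a Day 15 peak has both the Day 8 and the Day 21 draw in its window. Suppose, as an assumption, that offsets are independent and uniform on the whole days −3 to +3. The Day 21 draw falls outside the window when its offset exceeds the Day 15 offset by 2 or more: (5+4+3+2+1)/49 = 15/49 = 31%. The window holds only the peak-day draw in 20 of 343 combinations (5.8%). Unscheduled draws would lower both figures.

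**3. The five-patient trigger.** SAP 3.1 gives 18 + 9 = 27 enrolled, all taken here as treated. Five cases are 5/27 = 18.5%; four are 4/27 = 14.8% and give no table. The true case rate p is not in the documents, so a range is assumed, with X ~ Binomial(27, p):

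| p | P(X ≥ 5), table produced | P(1 ≤ X ≤ 4), cases but no table |
|---|---|---|
| 1% | 0.0% | 23.8% |
| 5% | 1.0% | 74.0% |
| 10% | 12.7% | 81.5% |
| 15% | 38.1% | 60.6% |
| 20% | 65.2% | 34.6% |

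This assumes that every case is recognised. The SAP seems to take the count from the plot, in which case missed patients also lower the count that triggers the table.

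**4. Whether another output covers the gap.** Shift tables treat each analyte separately and cannot show a pair. Listings contain the data but apply no paired criterion. The SMQ tables depend on an adverse event having been reported. None is a systematic search for ALT or AST >3x with bilirubin >2x ULN.

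**The case against.** - **The AST plot is a second anchor.** This stands in part: record C shows a rescue, and record B shows that there is none when AST and ALT peak together.
- **Record A is unusual.** Protocol 3.6.1 says laboratory values mostly returned to near baseline 14 to 28 days after the first infusion, and Protocol 3.6.2 calls the transaminase elevations mostly short-lived and not dose-limiting. This stands as a point about frequency. A safety screen exists for the unusual patient.
- **The data are not hidden.** Flagged patients appear on the plot, every value is listed, and patient safety during the trial does not rest on an end-of-study figure. This stands, and it rules out reading the gap as concealment. It does not provide a search.
- **The meaning of peak is open.** The SAP does not define its period, and the example figure is not available here. The whole-study reading is the plain one, but it remains an inference, so the period should be stated.

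Stronger readings are tempting, and the documents do not support them:

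- A reader might put a size on the miss rate by modelling a bilirubin lag, or by taking the Hy's Law cycle as equally likely to be any of k cycles (1 − 1/k, or 50% for two cycles and 83% for six). No document gives a bilirubin time course. Equal likelihood ignores that severe injury may also produce the highest ALT, and it ignores the AST plot.
- A reader might infer that up to four cases go unreported for want of the table. That table has only single-analyte categories, so it would not count Hy's Law cases even with five or more.
- A reader might take the count-once sentence to mean that AST, ALT and bilirubin elevations in one patient cannot all appear. The AST 11x example points to the worst category within a parameter.

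**Conclusion.** The concern holds in a limited form. Read literally, SAP 4.4.3 can miss patients who meet its own thresholds in a different cycle from the ALT peak, or more than 7 days after it, and it then plots them in the quadrant read as no significant hepatic abnormality. The AST plot catches some of them, and no other planned output applies a paired criterion. The conclusion rests on the plain reading of peak as one value per patient over the study.

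How many would be missed cannot be estimated from the documents. The constructed records show that misses are possible, not how common they are, and the trigger probabilities rest on assumed case rates. The five-patient threshold matters because it is the only count-based step after the plot and it leads to no count of candidates. The count-once wording needs only a clarification. The change is worth making because it is cheap and serves a primary objective.

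**What to change.** Keep both plots and amend SAP 4.4.3 as follows:

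1. State the period over which peak ALT and peak AST are taken.
2. Add a search of all scheduled and unscheduled post-baseline samples in every cycle. A candidate is any patient with ALT or AST >3x ULN and total bilirubin >2x ULN within a stated window either side of any qualifying ALT or AST value. The existing 7 days could serve, with a sensitivity search at any time on treatment.
3. Mark these patients on both plots. Report their number and percentage, with a by-patient listing, whatever the count. For scale, the exact two-sided 95% interval is 0.1% to 19.0% for 1/27 and 4.2% to 33.7% for 4/27.
4. Clarify that the single-analyte table counts a patient once per parameter, in the worst category. The five-patient condition must not govern the candidate count.

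The 7-day search finds records A and B, since each has a qualifying pair on one sample. It would still miss a bilirubin rise more than 7 days after the last ALT or AST above 3x ULN; the sensitivity search covers that. The cost is SAP wording and minor programming on laboratory data already collected. A few more patients will be flagged for medical review, some with unrelated bilirubin rises, especially in the sensitivity search.
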